1.3.2 Nonclinical Safety

Safety pharmacology studies revealed no effects related to central nervous system or respiratory function. In dogs, transient QTc prolongation was observed at 100 mg/kg/day and above, whereas no other findings related to cardiac function were reported.

A comprehensive repeated dose toxicology program has been conducted in rats and dogs. In rats dosed up to the limit dose of 1 g/kg/day, no relevant setanaxib-related toxicities were identified in any of the studies, whereas the no-observed-adverse-effect-level (NOAEL) was established at 150 mg/kg/day in the 26-week dog study and 300 mg/kg/day in the pivotal 39-week dog study. Treatment-related findings in the dog included electrocardiogram (ECG) (QT-prolongation) and effects on the erythrocyte and reticulocyte counts indicative of effects on bone marrow. Reductions in red blood cell parameters were observed in dogs exposed to high dose levels of setanaxib (≥ 500 mg/kg/day) after a few weeks of treatment. The affected dogs showed minimal (10% to 20%) red blood cell reductions, occasionally with a concomitant increase in hematopoiesis in the spleen and/or bone marrow, followed by a marked increase in circulating reticulocytes, and subsequent recovery towards normal levels. One female developed non-regenerative anemia and was euthanized. Apart from this female, dogs that were affected at high exposures generally tended

to recover following a dose reduction or upon cessation of dosing. Slight to moderate follicular cell hypertrophy of the thyroid was observed in some dogs of the 28-day and 13-week study, but no such change was observed in the 26- and 39-week studies despite comparable exposures. Hormone analysis of thyroid-stimulating hormone (TSH) and thyroxine (T4) revealed indications of low total T4 and high TSH levels in individual high dose animals sometimes correlating with the hypertrophy. Setanaxib has been investigated in a standard battery of mutagenicity tests and was found not genotoxic.

Rat and rabbit studies addressing fertility, early embryonic- and embryo-fetal development have been conducted. There was no evidence of any embryo-fetal toxicity, except for a lower mean fetal weight at the dose level of 1000 mg/kg/day in rats. No treatment-related malformations have been observed. In addition, sperm parameters have been found unaffected by setanaxib treatment. For further details, refer to the IB.

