1.6.2 Potential Risks

Setanaxib has been extensively investigated in nonclinical ([Section 1.3](#)) and clinical ([Section 1.4](#)) studies. Setanaxib has not previously been studied in adolescents. However, there have been no findings from toxicology studies indicating toxicity to organ systems potentially sensitive to disruptive effects during late childhood or throughout adolescence. Based on available and extensive information on the pharmacology of NOX1/4 inhibition in animals and phenotypic data from NOX1 and NOX4 KO animals, there are no indications of effects that could be considered detrimental to growth or maturation.

In the completed Phase 1 and Phase 2 studies, the safety profile of setanaxib has been shown to be acceptable, with no relevant clinical safety signals identified.

Patients included in this study will undergo regular safety assessments. In addition, given the findings from the toxicology studies and ongoing clinical studies, appropriate exclusion criteria and safety endpoints for regular monitoring have been built into this study as precautions.

- **Thyroid disorders (hypothyroidism):** Patients with uncontrolled hypothyroidism will be excluded from this clinical study. Patients with subclinical hypothyroidism may be included. Subclinical hypothyroidism is defined biochemically as a normal serum free T4 concentration

in the presence of an elevated serum TSH concentration. The levels of TSH and free T4 will be regularly monitored during the study.

- **Anemia:** Patients with a history of aplastic anemia, or any current marked anemia defined as hemoglobin <10.0 g/dL, AND absolute reticulocyte counts of <50% of the baseline value (Screening Study Visit 2), which is confirmed by repeat testing, will be discontinued from the study treatment. Reticulocyte counts will be regularly monitored during the study. In case of Common Terminology Criteria for Adverse Events (CTCAE) Grade ≥ 2 anemia, investigational medicinal product (IMP) administration will be interrupted while the patient undergoes further evaluation. See [Section 8.8.1](#) for more information regarding the detection and management of potential bone marrow toxicity.

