8.1.4 Adverse Events of Special Interest

The Investigator will monitor each patient for clinical and laboratory evidence of predefined AESIs throughout the patient's participation in this study.

The Investigator will assess and record any additional information on the AESI in detail on an AE eCRF, which must be completed within 24 hours of awareness of the event, following the same procedure as for serious AEs (SAEs) (see [Section 8.3](#)).

For this study, CTCAE Grade ≥ 2 anemia, defined as hemoglobin < 10 g/dL, AND absolute reticulocyte counts of $< 50\%$ of the baseline value (Screening Study Visit 2), which are confirmed by repeat testing, will be considered an AESI.

During the course of the study, additional AESIs may be identified by the Sponsor. AESIs must be recorded in the eCRF.

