8.8.1 Detection and Management of Potential Bone Marrow Toxicity

Particular attention will be given to the detection and management of potential cases of bone marrow toxicity. In case of Grade ≥ 2 severity anemia, the Investigator will instruct the patient to interrupt IMP administration and to return to the study site within 7 days so that the absolute reticulocyte count can be retested. If the retest value is below 50% of the baseline value (Screening Study Visit 2), IMP will not be resumed and will be permanently discontinued. IMP administration will be resumed only if the retest value of the absolute reticulocyte count is $\geq 50\%$ of the baseline value and a Grade ≤ 1 of anemia, and an alternative cause for the anemia can be documented. The patient will continue to be closely monitored (at least weekly) until normalization of the reticulocyte count, ie, return to baseline values.

Anemia will be reported to the Sponsor (or designee) as an AESI, as defined in [Section 8.1.4](#), following the same procedure as for SAEs ([Section 8.3](#)).

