3.4.1 Adverse Events -Primary Endpoint

The primary endpoints are:

- Percentage of patients with treatment-emergent SAEs;
- Percentage of patients with treatment-emergent AESIs.

All adverse events (AEs) will be coded to SOC and PT using MedDRA version v 26.1. Treatment-emergent adverse events (TEAEs) are defined as AEs that start after the first dose of study drug and up to 30 days post-last dose of study drug. Pre-treatment AEs are defined as AEs that started prior the first dose of study drug and post-treatment AEs are defined AEs that started more than 30 days after last dose of study drug.

AESI is defined as CTCAE Grade ≥ 2 anemia, defined as hemoglobin <10g/dL, and absolute reticulocyte counts of <50% of the baseline value (Screening Study Visit 2), which are confirmed by repeat testing.

Estimand

To assess the primary endpoint for treatment-emergent SAE, the safety estimand is defined by the following key attributes, according to the framework provided in International council for Harmonization (ICH) E9 (R1) [1]:

- **Treatment:** Setanaxib treated patients compared to placebo
- **Population:** The SAS comprised of all randomized patients who took at least 1 dose of the study drug.
- **Variable of interest:** Treatment-emergent SAEs
- **Intercurrent event handling:** All events will be counted regardless of early discontinuation of treatment, up to 30 days post-last dose of study drug
- **Summary measures:** Count and percentage of patients experiencing SAEs during the Treatment Period up to 30 days post-final dose.

The number and percentage of patients with SAEs will be presented by treatment group, system organ class (SOC), and preferred term (PT). Similar summaries will be presented for treatment emergent AESIs. The number and percentage of patients with study drug related treatment-emergent SAEs and AESIs will be presented by treatment group, SOC and PT.

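### The primary anaemia AESI needs a confirming repeat test, but the only reticulocyte retest described is taken after study drug is interrupted, so on-drug suppression that recovers by then can be scored as no AESI

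*SAP*

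**What the plan says.** SAP 3.4.1 lists "Percentage of patients with treatment-emergent AESIs" as a primary endpoint. The AESI is Grade 2 or worse anaemia, given as haemoglobin below 10 g/dL, "and absolute reticulocyte counts of <50% of the baseline value (Screening Study Visit 2), which are confirmed by repeat testing". Protocol 8.1.4 sets the same condition, for values "which are confirmed by repeat testing, will be considered an AESI", and Protocol 1.6.2 repeats it.

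The management passages fix the order of events. Under Protocol 8.8.1, when Grade 2 or worse anaemia is seen, "the Investigator will instruct the patient to interrupt IMP administration and to return to the study site within 7 days" for a reticulocyte retest. Protocol 1.6.2 agrees that study drug "administration will be interrupted while the patient undergoes further evaluation". A retest below half of baseline means permanent discontinuation (Protocol 4.3 and 8.8.1). Resumption requires three things together: a retest at half of baseline or more, anaemia of Grade 1 or less, "and an alternative cause for the anemia can be documented".

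Protocol 1.3.2 gives the background. Red-cell falls in high-dose dogs were "followed by a marked increase in circulating reticulocytes, and subsequent recovery towards normal levels". Apart from one euthanised female, affected dogs generally tended "to recover following a dose reduction or upon cessation of dosing".

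**The concern.** The retest that decides whether an AESI exists appears to be taken off drug. If the marrow effect reverses when dosing stops, the act of stopping can remove the event from the primary count. The SAP's estimand for SAEs counts events whether or not treatment was discontinued early. No estimand is written for the AESI, and nothing says how an interruption before confirmation is to be handled.

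Management and endpoint can then disagree. A patient whose reticulocytes recover but who has no documented alternative cause does not meet the conditions for resuming, yet adds nothing to the AESI percentage. At stake is how a low or zero AESI percentage is read when the results are used, as Protocol 1.5 intends, to plan later studies.

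**Working it through.** No power, alpha or expected event rate rests on this definition. Protocol 9.2.3 says the sample size was chosen empirically and SAP 3.1.6 rules out formal testing, so there is no plan figure to reproduce. The check traces the rules and then illustrates the size.

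**1. Tracing one patient.** Suppose a scheduled on-drug sample shows haemoglobin below 10 g/dL and reticulocytes below 50% of baseline.
- Protocol 8.8.1: drug is interrupted and reticulocytes are retested within 7 days.
- Retest below 50%: the AESI is confirmed and drug is permanently stopped. Endpoint and management agree.
- Retest at 50% or more: the AESI is not confirmed. Drug resumes only with Grade 1 or less anaemia and a documented alternative cause. Without that cause the patient stays off drug and is not counted.

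**2. Where the uncounted patient would appear.**
- SAP 3.4.2: TEAE tables overall and by maximum severity, and the discontinuation table if non-resumption is recorded as discontinuation. An event graded 2 is not in the Grade 3 or higher table, and no table of interruptions is listed.
- SAP 3.4.3: summaries by visit, counts outside the normal range, and clinically significant changes identified through TEAEs.
- SAP 3.3.7: exposure ignores interruptions.
- Protocol 8.2: blood dyscrasias are an example of an important medical event, so the case could enter the SAE endpoint if judged serious.

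No planned table isolates patients who met both criteria on the triggering sample.

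**3. Drug remaining at the retest.** Protocol 1.4.1 gives a single-dose half-life of about 8 to 14 h. Seven days is 168 h: 168/14 = 12 and 168/8 = 21 half-lives. A retest late in the window is essentially drug-free. This concerns plasma drug, not marrow recovery.

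**4. Size.** 18 patients at 2:1 gives 18 × 2/3 = 12 on setanaxib and 18 × 1/3 = 6 on placebo. One case is 1/12 = 8.3% or 1/6 = 16.7%.

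**5. Illustration.** Let p be the share of setanaxib patients meeting both criteria on the triggering sample, and q the share of those still below 50% at the retest. Both are assumptions; neither is in the documents. The chance of at least one AESI among 12 is 1 − (1 − pq)^12:

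| p | q = 1 | q = 0.75 | q = 0.5 | q = 0.25 |
|---|---|---|---|---|
| 10% | 72% | 61% | 46% | 26% |
| 20% | 93% | 86% | 72% | 46% |
| 30% | 99% | 95% | 86% | 61% |

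With 0 of 12 confirmed, the one-sided 95% upper bound on the confirmed rate is 1 − 0.05^(1/12) = 22%. As a bound on the triggering-sample rate it is that value divided by q: 29% at q = 0.75, 44% at q = 0.5 and 88% at q = 0.25. If all cases were still low at the retest (q = 1), nothing would be lost.

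**The case against.** The strongest defence is that requiring both low haemoglobin and confirmed low reticulocytes is a reasonable way to target non-regenerative anaemia, the pattern in the euthanised dog. Confirmation also screens out spurious low values in either arm, which matters when one false positive among about 6 placebo patients is 16.7%. Patients may enter with haemoglobin of exactly 10.0 g/dL, so small fluctuations can cross that threshold. All of this stands, and it is the reason to leave the primary definition alone. Rewording Protocol 8.1.4 would also change which events need 24-hour reporting and would need an amendment.

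Several stronger readings are tempting but not supported:
- *The toxicity is scored as no event at all.* It is only scored as no AESI; the other tables and unblinded IDMC review remain.
- *The endpoint captures mainly irreversible suppression.* Suppression need only last until the retest to count. Seven days is a maximum.
- *The dog data show a rebound within the retest window.* The reticulocyte rise is reported after red-cell falls during treatment and is not tied to stopping. The sentence on recovery after cessation gives neither a time course nor reticulocyte values.
- *The bias is confined to setanaxib.* Loss through drug reversal is, but removal of noise affects both arms.

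One uncertainty remains: the documents never say outright that the 8.8.1 retest is the AESI confirmation, or whether haemoglobin must also be confirmed. Reading it as the confirmation is natural, because it is the only reticulocyte retest described and 8.8.1 goes on to AESI reporting.

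**Conclusion.** The concern holds in a limited form. As written, on-drug suppression that meets both laboratory criteria but recovers by a retest taken after interruption can drop out of a primary endpoint, even when the patient stays off drug because no alternative cause is documented. This rests on the 8.8.1 retest being the confirming sample.

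The size of the loss cannot be estimated from the documents, since it depends on an unstated recovery time. One such patient moves the setanaxib percentage from 8.3% to 0%. If half of triggering cases recovered by the retest, the chance of seeing any AESI would fall from 72% to 46% at an assumed 10% rate. The gap is one of reporting and interpretation. It does not show that marrow toxicity would go unseen in the trial.

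**What to change.** Keep the confirmed AESI as the primary count. In SAP 3.4.1, before database lock, add to the same table, by arm:
- (a) patients whose triggering treatment-emergent sample meets both laboratory criteria, split into confirmed and not confirmed on the retest, with a footnote for any patient who had no retest;
- (b) patients with any treatment-emergent haemoglobin below 10 g/dL, regardless of reticulocytes.

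State beside the table that a confirmed AESI percentage of 0% does not exclude suppression that reverses when drug is interrupted.

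Separately, the sponsor should reconcile the AESI definition (Protocol 1.6.2 and 8.1.4, SAP 3.4.1) with the interruption and retest passages (Protocol 1.6.2, 4.3 and 8.8.1), so that it is clear which sample confirms the event and which values must be confirmed. No clinical or reporting rule is proposed here.

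The cost is a few lines of SAP text and the extra rows; haemoglobin and reticulocytes are already in the same haematology panel (Protocol Appendix B). The downside is that an occasional spurious low value will appear in a supportive row in either arm. For row (a), the split by retest result makes it visible.

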4.3 Withdrawal Criteria

A patient may prematurely discontinue study drug and/or withdraw from the study at any time. A distinction must be made between premature discontinuation of study drug and withdrawal from the study. A patient may prematurely discontinue study drug and still continue his/her participation in the study.

The reasons for premature discontinuation of study drug and for withdrawal from the study must be documented in the eCRF. Reasons for premature discontinuation of study drug include, but are not limited to, the following:

- Withdrawal of consent/assent;
- Any event, laboratory abnormality, intercurrent illness, or other medical condition that indicates to the Investigator that continued participation is not in the best interest of the patient;
- Pregnancy;
- Patient failure to comply with Protocol requirements or study-related procedures;
- Termination of the study by the Sponsor or regulatory authority;

- Initiation of medications known to be potent CYP3A4 inhibitors (itraconazole, lopinavir/ritonavir, telaprevir, clarithromycin, ritonavir, ketoconazole, indinavir/ritonavir, conivaptan, and voriconazole), potent CYP3A4 inducers (avasimibe, carbamazepine, enzalutamide, mitotane, nevirapine, phenobarbital, phenytoin, rifabutin, rifampicin, rifapentine, and St John's wort), or potent UGT1A9 inhibitors and inducers (mefenamic acid and rifampicin);
- The patient experiences mean QT prolongation (mean QTcF interval >500 milliseconds AND increase by >60 milliseconds over the mean baseline QTcF);
- Severe allergic reactions to the study drug;
- The patient has CTCAE Grade ≥ 2 anemia AND the retest absolute reticulocyte count is below 50% of the baseline value. In this case, study drug will not be resumed and will be permanently discontinued; or
- The patient has suspected DILI meeting [Criterion 3](#) in [Appendix C](#).

Unless a patient withdraws his/her consent/assent to participate in the study, all patients should be encouraged to complete the remaining study visits, regardless of whether they are still receiving study drug.

For patients who are withdrawn from the study prior to completion of Study Visit 8, the Early Termination Visit procedures will be completed, if possible, at the time the decision is made to withdraw the patient. The Early Termination Visit will consist of all of the Study Visit 8 procedures. The reason for patient withdrawal must be documented in the eCRF.

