8.1 Adverse Events

An AE is defined as any untoward medical occurrence in a patient administered a pharmaceutical product, which does not necessarily have a causal relationship with this treatment. An AE can therefore be any unfavorable and/or unintended sign (including a clinically significant abnormal laboratory finding), symptom, or disease temporally associated with the use of an IMP, whether or not related to the IMP. All AEs, including observed or volunteered problems, complaints, or symptoms, are to be recorded on the appropriate eCRF. The Investigator should update the appropriate eCRF if additional follow-up information becomes available (eg, the AE has subsided, stabilizes, or the condition becomes chronic in nature).

AEs, which include clinical laboratory test results, will be monitored and documented from the time of informed consent/assent until the end of the Follow-up Period (Study Visit 9). Patients should be instructed to report any event that they experience to the Investigator, whether or not they think the event is due to study drug. From the time of informed consent/assent, Investigators should make an assessment for AEs at each visit and record the event on the appropriate AE eCRF.

Wherever possible, a specific disease or syndrome rather than individual associated signs and symptoms should be identified by the Investigator and recorded on the eCRF. However, if an observed or reported sign or symptom is not considered a component of a specific disease or syndrome by the Investigator, it should be recorded as a separate AE on the eCRF. Additionally, the condition that led to a medical or surgical procedure (eg, surgery, endoscopy, tooth extraction, or transfusion) should be recorded as an AE, not the procedure itself.

Any medical condition already present at informed consent/assent should be recorded as medical history and not be reported as an AE unless the medical condition or signs or symptoms present at baseline change in severity, frequency, or seriousness at any time during the study. In this case, it should be reported as an AE.

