8.3 Serious Adverse Event Reporting – Procedures for Investigators

8.3.1 Initial Reports

All SAEs occurring from the time of informed consent/assent until 30 days after the last study drug dose must be recorded in the electronic data capture (EDC) and be reported to the Calliditas Patient Safety Mailbox at [contact] within 24 hours of the knowledge of the occurrence. Following 30 days after the last study drug dose, any SAE that the Investigator considers related to study drug must be reported to the Calliditas Patient Safety Mailbox.

To report the SAE, complete the Safety Report Form along with supporting documents if applicable (eg, laboratory reports, hospital discharge summaries, etc) and report to the Calliditas Patient Safety Mailbox at [contact] or call the Calliditas SAE reporting line, and email the completed paper Safety Report Form to Calliditas (contact information listed below) within 24 hours of awareness.

The Investigator is obliged to respond to any request for follow-up information (eg, additional information, event outcome, final evaluation, or other records where needed) or to any question the Sponsor (or designee) may have concerning the SAE within the same timelines as those noted above for initial reports. This is necessary to ensure prompt assessment of the event by the Sponsor (or designee) and, as applicable, to allow the Sponsor to meet strict regulatory timelines associated with expedited reporting obligations for events of this nature.

Calliditas SAE reporting line:
Telephone (Germany): [name]
Email: [contact]

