APPENDIX A: SCHEDULE OF PROCEDURES

Table 2. Schedule of Procedures

Study Period	Screening (4 Weeks)			Treatment Period (24 Weeks)								Follow-Up (4 Weeks) ^a
			2	N/A ^b								8 EOS/ ET ^d
Study Visit	1				3 ^c					7		9
Study Day or Week	See footnote ^e				Day 1	2w	6w	12w	18w	24w		28w
Visit Window (Days)		±7			+3	±3	±7	±7	±7	±7		±7
Study Procedures												
Genetic testing to confirm Alport syndrome diagnosis ^f	X											
Informed consent/assent ^g	X											
Demographics and medical/surgical history	X											
UPCR/eGFR history ^h	X											
Update medical/surgical history			X		X							
Eligibility criteria assessment	X		X	X								
Contact IRT to trigger study drug shipment and randomization				X								
Prior and concomitant medications and procedures ⁱ	X		X		X	X	X	X	X	X	X	X
AE assessment ^j	X		X		X	X	X	X	X	X	X	X
Physical examination ^k	X											
Hearing examination ^l		X										
Vital signs ^m	X		X		X	X	X	X	X	X	X	X
Body weight and height ⁿ	X		X		X	X	X	X	X	X	X	X
12-lead ECG ^o	X		X		X	X	X	X	X	X	X	X
Hematology ^p	X		X			X	X	X	X	X	X	X
Serum chemistry ^p	X		X			X	X	X	X	X	X	X
INR ^q		X										
FSH ^r			X									
TSH and free T4	X					X	X	X	X	X	X	X

Table 2. Schedule of Procedures (Continued)

Study Period	Screening (4 Weeks)			Treatment Period (24 Weeks)							Follow-Up (4 Weeks) ^a
	1	2	N/A ^b	3 ^c	4	5	6	7	8 EOS/ ET ^d		
Study Visit											
Study Day or Week	See footnote ^e			Day 1	2w	6w	12w	18w	24w		9
Visit Window (Days)	±7			+3	±3	±7	±7	±7	±7		±7
Study Procedures											
HIV, HBV, and HCV ^s	X										
Drug screen (urine)	X										
Supply 24-hour urine containers	2X				X	X		2X	X		
24-hour urine collection ^f		2X				X	X		2X	X	
UPCR		2X				X	X		2X	X	
eGFR ^u	X	X			X	X	X	X	2X	X	
Urinalysis ^v	X	X			X	X	X		X	X	
Biomarker sampling ^w		X					X		X		
Future analysis sampling		X					X		X		
PK sampling ^x					X		X		X		
Pregnancy test ^y		X		X	X	X	X	X	X	X	
Dispensing of study drug				X		X	X	X			
Start of study drug ^z				X							
Return of unused study drug					X	X	X	X	X ^{aa}		
Study drug accountability and compliance assessment ^{bb}					X	X	X	X	X		

Note: Prior to conducting any study-related activities, written informed consent/assent must be signed and dated by the patient and/or legally authorized representative or parent/guardian.

- Following completion of the Treatment Period, patients will enter a 4-week Follow-up Period.

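### The anemia AESI and non-serious TEAEs are counted to 30 days after the last dose, but scheduled collection ends nominally at day 28, and at the Early Termination visit for patients who leave the study

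*SAP*

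**What the plan says.** **Counting.** SAP 3.4.1 states for the SAE estimand: "All events will be counted regardless of early discontinuation of treatment, up to 30 days post-last dose of study drug". The same section defines TEAEs as "AEs that start after the first dose of study drug and up to 30 days post-last dose of study drug". That definition governs treatment-emergent AESIs and all non-serious TEAE tables. The SAE estimand in Protocol 9.2.1 uses the same 30 days.

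**Collecting AEs.** Protocol 8.1 documents AEs from consent "until the end of the Follow-up Period (Study Visit 9"). Visit 9 is at Week 28 ±7 days in Appendix A, and the last scheduled hematology is also there.

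**Collecting SAEs.** Protocol 8.3.1 has a separate rule, not tied to a visit: "All SAEs occurring from the time of informed consent/assent until 30 days after the last study drug dose must be recorded". Beyond that point, SAEs judged related to study drug are still reportable.

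**Leaving early.** Protocol 4.3 separates stopping study drug from leaving the study. Patients who only stop drug are encouraged to attend their remaining visits. For those withdrawn from the study before completing Visit 8, "the Early Termination Visit procedures will be completed, if possible, at the time the decision is made to withdraw the patient". That visit repeats the Visit 8 procedures. Footnote a of Appendix A says: "Following completion of the Treatment Period, patients will enter a 4-week Follow-up Period". Neither place states a visit or contact after Early Termination.

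**The concern.** The period over which events count and the period over which they are looked for should match. Here they do not, even for a completer seen exactly on schedule.

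The mismatch matters most for the AESI. It is a primary endpoint and is defined by laboratory results: hemoglobin below 10 g/dL and reticulocytes below 50% of baseline, confirmed by repeat testing. Without a blood sample it cannot be observed. Under SAP 3.1.8 safety data are used as available, without imputation, and the Safety Analysis Set includes everyone dosed. A patient not seen for part of the window therefore stays in the denominator as event-free. If study withdrawal differs between arms, so does post-dose observation.

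**Working it through.** **Inputs.** Target days from SAP 3.1.2: Week 24 = Day 169, Week 28 = Day 197. Windows from Appendix A: ±7 days for Visit 8 and for Visit 9. Last planned dose: the morning dose taken on site at Week 24 (Protocol 5.6.3), so at Visit 8. Counting window: 30 days (SAP 3.4.1). Group sizes: 18 patients at 2:1, so 18 × 2/3 = 12 and 18 × 1/3 = 6.

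**1. The plan's own figure.** Target day = 7 × week + 1, so 7 × 24 + 1 = 169 and 7 × 28 + 1 = 197. The difference is 28 days, which reproduces the 4-week Follow-up Period.

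**2. Completers.** Days from last dose to Visit 9, and the uncovered share, max(0, 30 − days)/30:

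- On target: 28 days; 2/30 = 7%.
- Both windows from Day 1, shortest: (197 − 7) − (169 + 7) = 14 days; 16/30 = 53%.
- Both windows from Day 1, longest: (197 + 7) − (169 − 7) = 42 days; 0%.
- Visit 9 timed from the actual Visit 8, shortest: 28 − 7 = 21 days; 9/30 = 30%.
- Visit 9 timed from the actual Visit 8, longest: 28 + 7 = 35 days; 0%.

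With both windows from Day 1 there are 15 × 15 = 225 pairs of whole-day offsets. In 134 of them Visit 9 falls before day 30. This counts what the windows allow; it is not a probability.

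**3. Scale against the whole at-risk period.** 168 + 30 = 198 days. On target, 2/198 = 1.0% is uncovered; in the shortest case, 16/198 = 8.1%.

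**4. Patients who leave the study.** If the last dose was k days before the Early Termination visit, scheduled assessment covers k of the 30 days. For a patient still on drug at that visit, k = 0 and all 30 days are uncovered.

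**5. SAEs.** Required recording is 30 days and counting is 30 days, so by rule the gap is 0 days. What is missing is a scheduled contact by which the site would learn of an event.

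**6. Weight of one event.** 1/12 = 8.3 percentage points on setanaxib; 1/6 = 16.7 on placebo.

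**The case against.** A reader might infer that both primary endpoints lack collection to day 30. The documents do not support that. Protocol 8.3.1 sets the SAE obligation at exactly 30 days, with no exemption for withdrawal, and deaths and hospitalizations often reach a site between visits.

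A reader might also infer that patients who stop treatment for safety reasons get no follow-up. Protocol 4.3 lists the QT, anemia, liver and allergy criteria as reasons to stop study drug, and Protocol 5.4 asks for data to Week 24 where possible. A patient who stops drug at Week 12 and stays in the study still has hematology at Weeks 18, 24 and 28. The zero-coverage case is confined to patients who leave the study while on drug. That such patients are more often safety cases is conjecture.

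Anemia already found is not lost: Protocol 8.8.1 requires a retest within 7 days and at least weekly monitoring, and the Early Termination visit includes hematology. Only anemia that first appears after the last sample is missed.

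The absence of a post-termination visit is read from silence. Visit 8 appears to supply a urine container for the Follow-up Visit, and Early Termination repeats Visit 8, so one could argue that follow-up is implied. The text is at best ambiguous.

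All of this stands and narrows the point. It does not remove it. AESIs share the SAE reporting procedure (Protocol 8.1.4), but a reporting route does not schedule a blood sample, and Protocol 8.1 still stops at Visit 9.

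**Conclusion.** The mismatch is real and modest. For the AESI and non-serious TEAEs, scheduled collection falls 2 days short of the 30-day window for a completer on target (7% of it). Across the permitted windows the shortfall is 0% to 53%, or 0% to 30% if Visit 9 is timed from Visit 8. The 53% figure is an extreme: Visit 8 at its latest and Visit 9 at its earliest. For patients who leave the study while on drug, no scheduled assessment covers any of the 30 days. For SAEs the rule is adequate, and only a scheduled contact is missing.

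This assumes that a completer's last dose is the Week 24 on-site dose and that the silence after Early Termination means no further contact. The documents give no rate of missed events or of withdrawal, so the number of lost events cannot be estimated. The analysis is descriptive, so no test is affected. The point deserves action because safety is the primary objective and one event moves an arm's percentage by 8.3 or 16.7 points.

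**What to change.** Reconcile Protocol 8.1, 8.3.1, 4.3 and Appendix A footnotes a and d with SAP 3.4.1, so that AE and AESI collection runs to at least 30 days after the last dose:

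1. Set the final AE assessment (Visit 9) no earlier than 30 days after the last dose. The Week 28 row of SAP 3.1.2 is open-ended above Day 197, so it already accommodates a later visit.
2. State that patients who leave before Visit 8 without withdrawing consent complete the existing Visit 9 assessments once 30 days have passed since their last dose, or at minimum an AE/SAE contact. A contact alone serves AEs and SAEs; observing a new AESI needs the Visit 9 hematology.
3. List in the CSR, by arm, every patient observed for less than 30 days after the last dose. This remains possible even if the protocol can no longer be amended.

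The SAP should add two clarifications: how an AESI first found on a sample drawn shortly after day 30 is classified, since the TEAE definition goes by start date, and how an early leaver's Visit 9 is labelled in by-visit tables.

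**Cost.** A small protocol amendment and a few SAP sentences. Visit 9 and its UPCR and eGFR samples move by a few days, and each early leaver adds one contact or one already-defined visit. No new procedure is needed.
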